3.3.5 Subject Assessments with the eDiary

Following randomization, subjects will report the following information in the eDiary:

- Details of the administration of CSL830 (i.e., dose, date, start time of injection, location of injection, and needle type used).
- Local reactions at the site of CSL830 administration (discomfort [e.g., pain, burning], swelling, bruising, itching) (yes/no).
- Prodromal symptoms experienced (fatigue, rash, muscle aches, nausea, tingling) (yes/no).
- HAE symptoms experienced (yes/no).
- Day and time of HAE symptom onset.
- Location of HAE symptom(s) from most severe to least severe (face/lips; tongue/inside mouth; throat/voice box; abdominal; genitourinary; extremities [right arm, left arm, right leg, left leg]).
- Location of primary HAE symptom (face/lips; tongue/inside mouth; throat/voice box; abdominal; genitourinary; extremities [right arm, left arm, right leg, left leg]).
- Severity of HAE symptom(s) (mild, moderate, or severe).
- Medication for the treatment of HAE attacks is needed (yes/no).
- If medication for the treatment of HAE attacks is needed:
 - Medication used (Berinert, Kalbitor, Firazyr, C1-INH other than Berinert, fresh frozen plasma, other).
 - Dose administered.
 - Day and time started.
 - Administration of medication by a health-care professional (yes/no).
- AEs (yes/no).
- Other concomitant medication (yes/no).

CCI

3.4 Study Analysis Populations

There will be six analysis populations defined for the study analyses:

3.4.1 Intent to Treat Population

The Intent to Treat (ITT) Population will comprise all subjects who provide informed consent/assent (as appropriate) and are randomized, regardless of whether or not they receive CSL830. Subjects in the ITT Population will be analyzed as randomized.

3.4.2 Safety Population

The Safety Population will comprise all subjects, who provide informed consent/assent (as appropriate), who are randomized, and who received at least 1 dose or a partial dose of CSL830. Subjects will be analyzed ‘as treated’, i.e., subjects in the Safety Population will be classified according to the actual treatment, regardless of the treatment assigned by randomization.

3.4.3 Per-Protocol Population

The Per-protocol (PP) Population will comprise all subjects in the ITT Population, excluding subjects who have a major protocol deviation. Protocol deviations will be reviewed and their impact assessed prior to database lock. See also [Section 4.11](#).

CCI [Redacted]

CCI [Redacted]

CCI [Redacted]

3.5 Discontinued Subjects

Subjects may withdraw from the study at any time at their own request, or they may be discontinued at any time at the discretion of the investigator or CSL for safety, behavioral or administrative reasons (e.g., due to an AE, protocol violation, loss to follow-up, subject noncompliance, and study termination). If CSL terminates the study premature, all subjects who are still participating in the study are regarded as discontinued from the study and “Study Terminated by Sponsor” will be entered as the reason for discontinuation.

Subjects who discontinue from the study prematurely at any time are considered discontinued subjects. Subjects who participated in the entire study and complete the Week 53 Visit according to protocol and who do not participate in the Extension Period are considered study completers even if they do not attend the Follow-up Visit after Week 53. Subjects who have continued treatment in the Extension Period and discontinued early in the Extension Period

are regarded as discontinued subjects. Subjects who complete the Extension Study and attend Extension Period Week 88 visit are considered study completers even if they did not attend the Follow-up Visit of the Extension Period.

In the event that a subject discontinues from the study, the investigator should record the reason and date of discontinuation in the eCRF and in the subject's medical records.

Subjects who discontinue participation in or are otherwise withdrawn from the study will not be replaced.

3.6 Randomization

A block randomization with 1:1:1-stratification for “CSL830-Continuation” Subjects, “CSL830-Interrupted” Subjects, and “CSL830- Naïve” Subjects will be used to ensure that subjects are randomized in balanced manner to a starting dose of CSL830 of either 40 IU/kg or 60 IU/kg.

Eligible subjects will be randomized to 1 of the 2 treatment groups (CSL830 40 IU/kg or CSL830 60 IU/kg) by means of Interactive Response Technology (IRT) according to the above mentioned randomization scheme. The IRT will assign the appropriate study treatment to each subject.

3.7 Blinding

Not applicable.

3.8 Sample Size

100 subjects are planned to complete the study. The sample size is based on guidelines issued by the International Conference on Harmonisation, ICH 1994 [1] and not on statistical calculations. The sample size of 100 subjects allows observation of ≥ 1 adverse event with a probability of 3% at 95% confidence.

4 Statistical Methodology

4.1 Planned Analyses

The data from Treatment Period 1, Treatment Period 2, and Extension Period will be analyzed and presented jointly, unless specified otherwise.

For subjects who are not participating in the Extension Period, the End of Study Visit will be at Week 53. For subjects who are participating in the Extension Period, the End of Study Visit will be at Week 88.

All summary tables will be presented by treatment groups 40 IU/kg CSL830, 60 IU/kg CSL830, and ≥ 40 IU/kg CSL830 unless specified differently. Events occurring under 80 IU/kg will be summarized in the ≥ 40 IU/kg CSL830 treatment group and otherwise listed only.

Subject disposition will be summarized for all subjects who provide informed consent/assent (as appropriate). Demographic and subject characteristics will be summarized using the ITT and Safety Populations.

All safety data will be summarized using the Safety Population. The analysis of the safety endpoints will be by actual CSL830 treatment (40 IU/kg CSL830, 60 IU/kg CSL830, or ≥ 40 IU/kg CSL830) the subject was taking when the event occurred, unless specified otherwise. In the analysis as treated, a subject contributes events or assessments to each treatment received, e.g. a subject randomized and treated with 40 IU/kg and up-titrated and treated with 60 IU/kg will be displayed in both treatments as well as displayed once in the ≥ 40 IU/kg treatment.

The efficacy endpoints considered as secondary will be summarized using the ITT and PP Populations. CCI

CCI

CCI

Continuous variables will be described by using the mean value with the respective 95% confidence intervals (CI) [only for efficacy variables]; standard deviation; range; 25th, 50th (median), and 75th percentiles; and counts of missing and non-missing values. The geometric coefficient of variation will be expressed as a percentage and the geometric mean and respective 90% CI will be calculated for CCI. The 90% CI for the geometric mean will be calculated by log transforming the data, calculating the lower and upper limits of the 90% CI of the mean of the log-transformed data and, subsequent back transforming the lower and upper limits. Categorical values will be described using counts and percentages. Time variables will be described by median, minimum and maximum and if applicable in addition by mean, standard deviation, 25th and 75th percentiles and graphically represented by Kaplan-Meier curves with the respective 95% CI.

All data will be displayed in by-subject listings. The listings will be sorted by treatment (40 IU/kg CSL830, 60 IU/kg CSL830, 80 IU/kg CSL830), site, subject, time point, and item number if applicable.

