11.3.3 Safety Analyses

The Safety Population will be used for analyses of safety.

Treatment Period 1 and Treatment Period 2

All subjects in the Safety Population will be included in the safety analyses. The primary safety analysis will be performed by treatment group (ie, subjects who are randomized to 40 IU/kg CSL830 and by subjects who are randomized to 60 IU/kg CSL830). Data collected from those subjects will be included in the 40 IU/kg and 60 IU/kg CSL830 treatment groups, respectively, until the time they undergo the final study visit or they undergo a CSL830 dose increase, whichever comes first.

A secondary safety analysis will be performed by treatment group [ie, subjects who are randomized to 40 IU/kg CSL830 and by subjects who are randomized to 60 IU/kg CSL380, regardless of any dose increase(s)]. Data collected from those subjects will be included in the

40IU/kg and 60IU/kg CSL830 treatment groups, respectively, until the time they undergo the final study visit.

The analyses will be done both for Treatment Period 1 (only) and for Treatment Period 1 and 2 (together), unless otherwise noted.

Furthermore, safety analyses will be summarized by subjects who are randomized to 40 IU/kg CSL830 and who have 1 dose increase; by subjects who are randomized to 40 IU/kg CSL830 and who have 2 dose increases; by subjects who are randomized to 60 IU/kg CSL830 and who have 1 dose increase.

After the dose increase, data collected from subjects who undergo a 20 IU/kg dose increase from 40 IU/kg to 60 IU/kg or from 60 IU/kg to 80 IU/kg in Treatment Period 1 will be summarized separately for the 60 IU/kg and 80 IU/kg CSL830 doses. Furthermore, data collected from subjects who undergo a 20 IU/kg dose increase from 40 IU/kg to 60 IU/kg or from 60 IU/kg to 80 IU/kg in Treatment Period 2 will also be summarized separately for the 60 IU/kg and 80 IU/kg CSL830 doses.

After a second dose increase, data collected from subjects who undergo a 20 IU/kg x 2 dose increase from 60 IU/kg to 80 IU/kg in Treatment Period 1 will be summarized separately for the 80 IU/kg CSL830 dose. Furthermore, data collected from subjects undergo a 20 IU/kg x 2 dose increase from 60 IU/kg to 80 IU/kg in Treatment Period 2 will also be summarized separately for the 80 IU/kg CSL830 dose.

Subjects who undergo a CSL830 dose increase will be flagged in the listing

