11.3.3.1 Primary Safety Analysis

The person-time incidence rate of each primary endpoint safety event will be assessed as defined above in [Section 11.3.3](#) and overall. The person-time incidence rates are the number of subjects experiencing each primary endpoint safety event during the respective treatment duration with CSL830, divided by the sum of each subject's time at risk in the respective treatment. The person-time incidence rate of each primary endpoint safety event will be assessed for Treatment Period 1 and for the Treatment Periods 1 and 2 overall. For the subjects who are in the Extension Period, the person-time incidence rate of each primary endpoint safety event will also be assessed for the Extension Period and for the treatment periods overall.

Adverse events will be classified using the Medical Dictionary for Regulatory Activities (MedDRA).

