4.7 Safety Analysis

Safety endpoints will be analyzed using the Safety Population as described in [Section 4.1](#).

AE will be classified using the Medical Dictionary for Regulatory Activities (MedDRA) version 18.0.

AEs which have a start date and time on or after the first injection date and time of CSL830 in study CSL830_3002 are considered treatment-emergent AEs. AEs with missing or partial start date or time will also be considered treatment-emergent following the worst case principle unless the partial date clearly indicates that the AE started before first injection date and time.

Only treatment-emergent AEs will be summarized in tables as described in [Section 4.1](#). AEs occurring after the Week 53 Visit and before the Follow-up Visit of Treatment Period 2 or the first visit of the Extension Period will be assigned to Treatment Period 2. AEs occurring between the Extension Period completion visit and the Extension Period Follow-up Visit will be assigned to the preceding treatment of the Extension Period.

Subgroup analyses will be performed for

- Use of any oral Prophylaxis for Treatment of HAE during the study
- Subject roll-over classification (“CSL830-Continuation” Subjects, “CSL830-Interrupted” Subjects, and “CSL830-Naïve” Subjects)

The subgroup “Subjects who use oral agents for the prophylactic treatment of HAE during the study” will only include subjects who are taking their prophylaxis according to protocol.

Notes:

- The above described subgroup analyses will only be done for
 - the overall AE tables for summary measures of safety
 - the primary safety endpoints by actual treatment
- Categories of subgroups will be presented in tables only if there are a minimum number of subjects in the subgroup ($n \geq 5$).
- If a causality assessment is not provided for an AE, that AE will be considered related to the investigational product. A subject having related and unrelated AEs will be counted once in each category, related and unrelated.
- Missing severity or outcome will be classified as “severe” or “not recovered”, respectively.
- A subject having AEs with different severities will be counted once in each severity category.
- A subject with more than one occurrence of the same AE PT will be counted once in the total count for that AEs PT. Similarly, a subject with one or more AEs in a particular SOC will be counted once in the total for that SOC.

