- i. the number of subjects experiencing a given primary endpoint safety event during treatment with an actual dose of CSL830 divided by the sum of each subject's time at risk while receiving that actual dose of CSL830. The "time at risk" (in years) is calculated per subject as:

(Date the subject experiences the first event, a CSL830 dose increase, or either CSL830 discontinuation or study completion (whichever is first) while taking a given, actual dose of CSL830 – date of the subject's first injection of the given, actual dose of CSL830 + 1)] / 365.25.

- ii. the sum of each subject's total number of events of a given primary endpoint safety event during treatment with an actual dose of CSL830 divided by the sum of each subject's time at risk while receiving that actual dose. The "time at risk" (in years) is calculated per subject as:

(Date the subject undergoes CSL830 dose increase or either CSL830 discontinuation or study completion (whichever is first) while taking the given, actual dose of CSL830 – date of the subject's first injection of the given, actual dose of CSL830 + 1)] / 365.25.

A subject accrues events over the time during which that subject receives a given actual CSL830 dose while participating in the study. If a subject undergoes a dose increase during the study and that subject experiences events during treatment with each respective dose of CSL830, such a subject contributes events in each treatment received. A subject randomized to 40 IU/kg and up-titrated to 60 IU/kg will be displayed in both treatments as well as in the ≥ 40 IU/kg treatment based upon their corresponding duration in that treatment.

The 95% CI will be calculated for each of the above described person-time incidence rates using the following formula:

$$\text{Lower CI} = \frac{k}{T} \chi^2(2 * Y, 0.025)/2$$

$$\text{Upper CI} = \frac{k}{T} \chi^2(2 * Y + 2, 0.975)/2$$

with

k = factor to normalize for annual rate which is equal to 1

T = sum of time at risk [years] over subjects calculated as described in the bullet points above.

For the person-time incidence rates described above in i.:

Y = number of subjects who experienced the safety event

For the person-time incidence rate described above in ii.:

Y = number of safety events

A by-subject listing will be produced showing the information if a subject has each primary endpoint safety event.

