4.14 Changes in Conduct or Planned Analyses from the Protocol

The statistical analysis for the original protocol and the Extension Period amendment are described in the one SAP to be on hand and not in two different statistical analysis plans.

The data from Treatment Period 1, Treatment Period 2, and Extension Period will be analyzed and presented jointly. Data collected from subjects who are enrolled in the Extension Period will be analyzed together with the data of subjects who are not participating in the Extension Period.

Because of the assumption that a minority (e.g., less than 20%) of subjects will undergo a CSL830 dose increase during the study, the first and second approaches as specified in 11.3.3 of the protocol will not be performed for the secondary safety endpoints. Rather, the approach to safety analysis based upon the actual treatment (40 IU/kg CSL830, 60 IU/kg CSL830 and ≥ 40 IU/kg CSL830) at the time of the event will be performed for the safety analyses.

The analyses by subjects who are randomized to 40 IU/kg CSL830 and who have 1 dose increase; by subjects who are randomized to 40 IU/kg CSL830 and who have 2 dose increases; by subjects who are randomized to 60 IU/kg CSL830 and who have 1 dose increase will not be done.

A treatment group ≥ 40 IU/kg CSL830 has been added in the analyses by treatment and overall group has been deleted.

If an event or evaluation occurred while a subject was receiving 80 IU/kg, these data will be listed and summarized in the ≥ 40 IU/kg CSL830 treatment group.

Adverse events that occur during the Screening will not be summarized for subjects in the Safety Population and will only be listed.

Safety and some efficacy analyses will not be performed for age group. No subgroups of subjects who previously used intravenously administered C1-INH for routine (long-term) prophylaxis will be assessed.

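### On the SAP text, no table directly shows the event rate or person-years at 80 IU/kg, the highest permitted dose, although the protocol plans separate safety summaries there

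*SAP*

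**What the plan says.** **Protocol.** Section 3.2 allows increases in 20 IU/kg steps to a maximum of 80 IU/kg: two steps from the 40 IU/kg arm, one from the 60 IU/kg arm. Section 11.3.3 defines the primary safety analysis by randomized dose, with a subject's data counted only until an increase. It then adds further summaries. Data after an increase in Treatment Period 1 are to be shown separately at 60 and 80 IU/kg, and data after an increase in Treatment Period 2 "will also be summarized separately for the 60 IU/kg and 80 IU/kg CSL830 doses". Second increases to 80 IU/kg get their own summary. Section 11.3.3.1 then says: "The person-time incidence rate of each primary endpoint safety event will be assessed as defined above in" Section 11.3.3, and overall, with the denominator being "time at risk in the respective treatment".

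**SAP.** Section 4.1 sets the default columns for all summary tables at 40, 60 and ≥40 IU/kg, unless specified differently. For the highest dose: "Events occurring under 80 IU/kg will be summarized in the ≥ 40 IU/kg CSL830 treatment group and otherwise listed only". Section 4.7 refers back to 4.1. Section 4.7.1 defines three groupings for the primary rates, of which the third goes by actual dose, with time at risk counted "while taking a given, actual dose of CSL830". It names no 80 IU/kg group, and its worked example covers only 40, 60 and ≥40. Section 4.14 lists the change among departures from the protocol: for events or evaluations at 80 IU/kg, "these data will be listed and summarized in the ≥ 40 IU/kg CSL830 treatment group". The nearest stated reason opens: "Because of the assumption that a minority (e.g., less than 20%) of subjects will undergo a CSL830 dose increase during the study".

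**The concern.** The primary objective is long-term safety, and 80 IU/kg is the top of the permitted range. The earlier experience above 60 IU/kg that the protocol describes is short: up to 120 IU/kg for 4 weeks (Protocol 7.5). The ongoing pivotal study uses only 40 and 60 IU/kg (Protocol 1.2.3).

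Of the SAP's three groupings, approach 1 drops events after an increase and approach 2 assigns them to the randomized dose. That leaves the ≥40 column of approach 3 as the only tabulated rate that includes 80 IU/kg as an actual dose. On the assumption that a minority of subjects escalate, that pool is mostly 40 and 60 IU/kg time. A tight pooled limit could then be taken as reassurance about a dose that contributed little of the exposure.

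**Working it through.** **Plan's own figure.** The only design figure is that 100 subjects allow at least one event of 3% probability to be seen with 95% confidence (Protocol 11.1, SAP 3.8). Check: 1 − 0.97^100 = 0.952, so it reproduces. This point does not depend on it, and neither document gives a figure for 80 IU/kg.

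**What can be recovered from the planned output**

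- *Subjects reaching 80 IU/kg.* SAP 4.3 tabulates subjects with one and two increases by treatment. If shown by randomized arm, one increase from 60 plus two from 40 gives the number.
- *Exposure.* SAP 4.4.1, item 3, summarizes exposure by actual treatment. Exposure adds across doses, so time at 80 = (≥40) − (40) − (60), if totals are printed or rebuilt from mean × n. This is close to, but not the same as, the rate denominator: 4.4.1 stops at Week 53 or Extension Week 88, while 4.7.1 takes study completion as the latest Follow-up Visit.
- *Event-based rate (ii).* Events and time both add across doses, so the same subtraction works if both are printed.
- *Listings.* Listings are sorted with 80 IU/kg as its own category (4.1). There are by-subject listings of injections (4.4.1), primary endpoint events (4.7.1), and up-titrated doses with solicited AE counts at each dose (4.7.2.1).
- *Subject-based rate (i), the protocol's definition.* Take a subject with an event at 60 IU/kg who escalates and has another at 80. The 60 column counts 1. A true 80 column would also count 1. The pool, taken as showing each subject once with time stopped at the first event, counts 1. Subtraction gives 1 − 1 = 0 at 80, when the answer is 1, and the time at 80 is lost as well. A subject with events at both 40 and 60 who never reaches 80 gives 1 − 1 − 1 = −1. Subtraction is exact for an endpoint with no events at all, but in general it fails once escalated subjects have events.

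**Illustrative size.** Inputs: 100 completers, 52 weeks (364 days) plus a 14-day follow-up, and 50 extension subjects with a further 88 weeks (616 days).

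Pool T = (100 × (364 + 14) + 50 × 616) / 365.25 = 68,600 / 365.25 = 187.8 person-years, about 188.

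Exposure at 80 IU/kg is assumed. Suppose 9 subjects escalate to 80 IU/kg at Week 25:

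- staying to Week 53: 9 × 28 × 7 / 365.25 = 4.8 person-years;
- staying to Extension Week 88: 9 × 116 × 7 / 365.25 = 20.0 person-years.

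The figures of 5 and 20 below are therefore examples, not bounds. The true exposure could be zero.

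SAP 4.7.1 limit with zero events: upper = χ²(2, 0.975) / 2 / T = 3.689 / T. With two events, both at 80 IU/kg and none elsewhere: rate = 2 / T.

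| Column | T (person-years) | Zero-event upper 95% limit, per year | Rate with two events, per year |
|---|---|---|---|
| 80 IU/kg, assumed | 5 | 0.74 | 0.40 |
| 80 IU/kg, assumed | 20 | 0.18 | 0.10 |
| ≥40 IU/kg pool | 188 | 0.020 | 0.011 |

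The 80 IU/kg share of the pool is 5/188 = 2.7% or 20/188 = 10.6%. The dose-specific limit is wider than the pooled one by 188/5 = 38 times or 188/20 = 9 times.

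**The case against.** **The protocol may not plan primary rates at 80 IU/kg.** A reader might infer that it does. The documents do not settle this. Section 11.3.3 names the randomized-dose analysis, cut off at an increase, as the primary one. The 60 and 80 IU/kg summaries come later and do not mention person-time. The cross-reference in 11.3.3.1 could point only to the named primary analysis. The safety paragraph of the synopsis groups escalated subjects by arm and number of increases, with no 80 IU/kg group. This objection stands: what is certain is a plan for separate safety summaries at 80 IU/kg, and applying them to the rates is one plausible reading. The SAP also keeps the protocol's primary and secondary groupings as approaches 1 and 2, and 4.14 records the actual-dose rates as an addition.

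**The change is declared.** It is, in SAP 4.14, so a reader who infers a hidden contradiction or lost data would be wrong. The reason about few escalations is written for the secondary safety endpoints, but its paragraph ends with the actual-dose columns for the safety analyses, so it may be meant more widely. It does not show that an 80 IU/kg column would be empty: just under 20% of about 110 subjects is up to 21 with an increase (0.20 × 110 = 22), although how many would go beyond 60 IU/kg is unknown.

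**The information is available elsewhere.** Largely true, as the working shows, and for a handful of subjects a listing can say more than a rate. What is left is that no table states the rate, its interval or its denominator directly.

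**The column would be sparse and confounded.** Also true. Subjects reach 80 IU/kg because of frequent attacks and at the investigator's discretion. This argues for a descriptive column with a caution and a display threshold. It does not make the pooled figure informative about 80 IU/kg.

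**The shells might include it.** They are a separate document (SAP 5.3), and 4.1 allows exceptions, so the point is limited to the SAP text.

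**Conclusion.** The point holds as a gap in reporting. Separate safety summaries at the highest permitted dose are in the protocol and have been replaced, with disclosure, by a pooled column and listings. On the SAP text no table directly shows the event rate or person-years at 80 IU/kg, even though approach 3 is defined by actual dose. No primary estimate changes and no data are lost. The subject count, the exposure and the event-based rate may be recovered, but the subject-based rate generally cannot be recovered from the tables once escalated subjects have events.

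The size depends on assumed exposure. With the planned numbers and time at risk to the Follow-up Visit, a zero-event endpoint would show an upper limit near 0.02 per year in the pool, where 5 to 20 assumed person-years at 80 IU/kg would support only 0.74 to 0.18. This is an optional, inexpensive improvement.

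**What to change.** Add a descriptive 80 IU/kg column to the approach 3 table in SAP 4.7.1 (subjects, events, person-years, rate and exact 95% interval by the existing formula) and to the AE overview in SAP 4.7.2.1. Show it when at least 5 subjects received 80 IU/kg. That threshold is borrowed by analogy: SAP 4.7 says "Categories of subgroups will be presented in tables only if there are a minimum number of subjects in the subgroup", with n ≥ 5, but that rule covers subgroup categories and not dose columns. Below the threshold, footnote the number of subjects and the person-years at 80 IU/kg.

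Add a footnote that escalation follows frequent attacks and investigator discretion, so the column is not a dose comparison.

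The cost is one extra column in two outputs, from data already collected and listed. The downside is wide intervals and confounding by indication, above all for HAE attacks leading to hospitalization.
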